Phase 2: A total of 70 adults diagnosed with COPD will be enrolled in the study. Half of the participants will be randomized to receive the home-based PR with the mindful breathing module which consists of the Pursed Lipped Breathing Application and the Spire Health Tags (intervention) and half will receive the home-based PR (control). Randomization will be take place in a REDCap database and will be in equal proportion.

Both groups entail one week of baseline where the participants wear an ActiGraph activity tracker and answer questionnaires. Baseline is followed by 12 weeks of home-based PR plus health coaching. The Intervention group also has the mindful breathing module loaded on the Android tablet. Both groups will also complete questionnaires and wear an ActiGraph activity monitor at 3 and 6 months.

Please see Figure 3 for a diagram of the intervention and Figure 4 for a diagram of the control scheme.

Questionnaires:

Quality of Life will be assessed three times (baseline, 3 and 6 months) by the Medical Research Council (mMCR) questionnaire, the Chronic Respiratory Disease Questionnaire (CRQ), the Self-Management Ability Scale (SMAS30) and the Mindful Attention and Awareness Scale (MAAS). The questionnaires take about 20 minutes to complete.

At baseline additional health data will be collected from the medical record (chart review) to complete the Charlson comorbidity index, including lung function, demographics, living condition (living alone or not), GOLD stage, and comorbidities.

ActiGraph:

Physical activity will be measured three times (baseline, 3 and 6 months) by the ActiGraph activity monitor. The ActiGraph activity monitor has tri-axial accelerometers and will be wrist worn for seven days. See Figure 5. Important measures to be analyzed are daily number of steps, activity counts, minutes per day spent in daily physical activities of at least moderate intensity, and sedentary time (<2 metabolic equivalents).

Figure 5

The questionnaires and Act Graphs will be mailed to the participant with pre-paid shipping materials to send back.

Health Coaching:

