All participants will receive a weekly coaching call to discuss their rehabilitation and health process. The calls are structured using motivational interviewing. The coach will review with the patient the data from the health coach system. Collaboratively, goals for rehabilitation for the following week will be set, based on information gathered and the patients' personal preferences. Each call lasts about 20 minutes. All calls will be taped to ensure compliance with the protocol.

Subject Information

Target accrual: 140

Subject population (children, adults, groups): Adults 40 years of age or older

Inclusion Criteria:

- Clinical diagnosis of COPD
- At least 10 pack years of smoking

Exclusion Criteria:

- Unable to do mild exercise (orthopedic-neurologic problems or confined to a bed)
- Unable to follow commands (cognitive impairment)
- Have a high likelihood of being lost to follow-up (active alcohol or drug abuse)
- Live in an area that does not have cellular service (Verizon)

Potential participants will have the option of meeting a study coordinator in person (if they are on campus for a clinical appointment), meeting via Video Anywhere through Epic, or meeting over the phone. If the patient desires, their consent can be digitally obtained and documented through PTRAX. The patient also has the option of receiving the consent via mail and mailing back the consent in a provided postage paid envelope. Documentation of informed consent/HIPAA authorization will involve the use of the Research Participant Tracking (PTrax) Digital Signature Capture technology for research informed consent/HIPAA authorization only while the subject, and/or the subject's representative, is in the physical presence of the person authorized to obtain consent/HIPAA authorization. The study team may print a copy of the signed consent form/HIPAA authorization form for the subject or their representative. The consent form/HIPAA authorization form will also be available to the subject via the patient portal. Note: If the subject or their representative prefers not to use the Digital Signature Capture technology, the study team will provide a paper consent form/HIPAA authorization form for signature.

Review of medical records, images, specimens

The study involves data that exist at the time of IRB submission **and** data that will be generated after IRB submission. Include this activity in the Methods section.

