The study plans to conduct a retrospective chart review and ask subjects to complete a questionnaire.

Data Analysis

Sample Size

We calculated that sixty two participants will provide 80% power to detect 1 point of change in the two co primary outcomes (breathlessness and emotion as measured by the CRQ) with an alpha of 0.025. A 1 point change represents a clinically meaningful change.95 We expect about a 20 percent attrition rate (withdraw, not able to complete the 12 weeks of home-based rehab) and will therefore enroll 70 participants in each phase.

Analysis Plan

The primary outcomes of the study are changes in breathlessness and emotions. Changes from baseline to three months on the two primary outcomes will be compared between the study arms using two-sample, two-sided t-tests with 5% type I error rates. Means, SDs, medians, ranges, and frequency distributions will be reported and plotted over time by study arm. Linear models will be used to assess the impact of treatment arm on three-month outcomes after adjusting for the corresponding baseline measure and other variables related to the outcome (age, degree of breathlessness at baseline using the mMRC dyspnea, and FEV1).

The Chronic Respiratory Disease Questionnaire (CRQ) is a 20-question inventory assessing the areas of dyspnea, fatigue, emotion, and feelings of mastery. The fatigue, emotion, and mastery subscales ask patients to rate how often in the last two weeks they have been afflicted with a particular feeling or experience on a scale of 1 to 7, with higher ratings indicating less symptom impairment. The CRQ has shown to be valid and has high internal consistency reliability. Test-retest reliability is adequate in all subscales, but is particularly high in the subscales of fatigue (r=0.90), emotion (r=0.93), and mastery (r=0.91). The minimal clinically important difference for this instrument of 0.5 points is universally recognized. The Domains Dyspnea (breathlessness) and Emotions are the two co primary outcomes.

Physical activity will be measured at baseline, 3, and 6 months by the ActiGraph GX6 activity monitor, which has been used to assess physical activity in COPD populations. (92) The number of daily steps at baseline, 3,

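### The primary test of each CRQ domain is an unadjusted t-test on change, which is valid but less efficient than the baseline-adjusted model planned in the same paragraph, and that model has no stated role

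*Combined protocol and SAP*

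**What the plan says.** The Analysis Plan, and an identical paragraph under Aims, purpose, or objectives, sets the primary comparison: "Changes from baseline to three months on the two primary outcomes will be compared between the study arms using two-sample, two-sided t-tests", with a 5% type I error rate. The outcomes are two CRQ domains: "The Domains Dyspnea (breathlessness) and Emotions are the two co primary outcomes".

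After a sentence on descriptive summaries, the same paragraph continues: "Linear models will be used to assess the impact of treatment arm on three-month outcomes after adjusting for the corresponding baseline measure". The further covariates are "age, degree of breathlessness at baseline using the mMRC dyspnea, and FEV1". This model estimates the arm effect on the same outcomes at the same visit. It is not labelled primary, supportive or sensitivity, and nothing says which result governs if the two disagree.

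The Sample Size section states that "sixty two participants will provide 80% power to detect 1 point of change in the two co primary outcomes" "with an alpha of 0.025". It enrols 70 per phase, allowing for about 20% attrition.

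On the source of FEV1, the Questionnaires section says: "At baseline additional health data will be collected from the medical record (chart review) to complete the Charlson comorbidity index, including lung function". The diagnostic entry criterion is "Clinical diagnosis of COPD", with no spirometry requirement. No rule covers a missing covariate.

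**The concern.** A t-test on change fixes the slope of the three-month score on baseline at 1. The linear model estimates that slope. Whenever the true slope differs from 1, the change score carries avoidable noise. Baseline CRQ is scheduled for both arms and is already needed to compute change, so adjusting for it loses no further participants. Each phase is small, so precision matters.

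Two further points follow. With the model's role unstated, two analyses of each primary outcome sit side by side with no rule for choosing between them. And the model as written cannot simply be promoted to primary: it includes FEV1 taken from the chart, and a complete-case fit would drop anyone without a recorded value.

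**Working it through.** **Inputs from the documents.** 62 participants, 1 point, 80% power, alpha 0.025 (Sample Size); two-sided tests at 5% (Analysis Plan); equal allocation; 70 enrolled per phase with about 20% attrition, so 70 × 0.8 = 56 evaluable, or 28 per arm.

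**Not in the documents.** The SD of change, and the correlation r between baseline and three months. The r = 0.93 quoted for Emotion is test-retest reliability, not a three-month correlation in treated patients. With a change SD of 1.25 it would imply a raw SD of 3.34, which is impossible on a 1 to 7 scale. I use r = 0.5, 0.7 and 0.8.

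**The plan's own figure.** Without an SD, 62 cannot be reproduced, so I solved for the SD it implies. With 31 per arm, difference 1, two-sided 0.025 and 80% power, the noncentral t gives a change SD of 1.250 (normal approximation 1.277). I use 1.25 as the main case and 1.0 to 1.5 as a range.

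**Variance ratio.** With equal variance s² at both visits:

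- Var(change) = 2(1 − r)s²
- Var(adjusted) = (1 − r²)s²
- ratio = (1 + r)/2 = 0.75, 0.85 and 0.90 at r = 0.5, 0.7 and 0.8

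The ratio is below 1 for every r below 1. A change SD of 1.25 implies a raw SD of 1.25/√(2(1 − r)) = 1.25, 1.61 and 1.98.

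**Power at 28 per arm, 1-point difference, change SD 1.25** (simulation, 120,000 trials per r):

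| Analysis | r = 0.5 | r = 0.7 | r = 0.8 |
|---|---|---|---|
| *Alpha 0.025* | | | |
| t-test on change | 75.1% | 75.1% | 75.1% |
| Arm + baseline CRQ | 86.4% | 81.4% | 78.9% |
| Same + three non-prognostic covariates | 84.1% | 78.8% | 76.2% |
| Last row, 4 of 56 dropped for missing FEV1 | 80.6% | 74.9% | 72.4% |
| *Alpha 0.05* (t-test 83.5–83.7%) | | | |
| Arm + baseline CRQ | 91.9% | 88.4% | 86.5% |
| Same + three non-prognostic covariates | 90.3% | 86.4% | 84.5% |

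The closed-form calculation for arm plus baseline CRQ at alpha 0.025 gives 87%, 82% and 80%. It is about one point higher because it ignores chance baseline imbalance. For the same reason, three non-prognostic covariates cost 2 to 3 points, more than the lost degrees of freedom alone would suggest.

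**Range over SD** (alpha 0.025, baseline CRQ only, same three r): at SD 1.0, 92% rises to 97%, 95% and 94%; at SD 1.5, about 58% rises to 71%, 64% and 62%.

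**Validity.** Simulated type I error at r = 0.5 and 0.7 was 0.023–0.025 (nominal 0.025) and 0.049–0.050 (nominal 0.05) for the t-test and both models.

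**Effect of the unstated role.** If success on a domain could be claimed from either the t-test or the baseline-adjusted model, each at 0.025, the per-domain type I error at 31 per arm is 0.037 (r = 0.5) or 0.036 (r = 0.7).

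**The case against.** The strongest reply is that nothing here is an error. Both analyses are valid, the t-test matches a sample size framed as change, and the paragraph ties the primary outcomes and the error rate to the t-test. The adjusted model will be run anyway. This stands as far as it goes: the t-test is the natural reading of the primary analysis. It does not answer the efficiency point, because the headline result would still come from the weaker analysis.

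Second, the gain depends on holding the change SD at 1.25. If the raw SD is held at 1.25 instead, t-test power at alpha 0.025 is already 94% at r = 0.7 and 99.1% at r = 0.8, and adjustment adds about 3 points or less. That is correct. But the change SDs are then 1.25 × √(2 × 0.3) = 0.97 and 1.25 × √(2 × 0.2) = 0.79. By the normal approximation even an SD of 1.0 needs only 40 in total, so this case does not fit the plan's own 62.

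Third, equal variances are assumed. If the three-month SD is 1.2 times baseline (change SD still 1.25, alpha 0.025), baseline-only power is about 81%, 76% and 74% at r = 0.5, 0.7 and 0.8, against 75%. So the gain is not guaranteed. At worst, power is about level, and a smaller three-month SD would enlarge the gain.

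Fourth, at alpha 0.05 the t-test already exceeds 80%. This is true under the same assumptions, but the Sample Size section uses 0.025. That conflict is a separate matter.

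Fifth, missing FEV1 is conjecture, since the plan intends to draw lung function from every participant's record. The 4 of 56 is indeed only an illustration. It is a caution about promoting the full model, not a prediction.

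**Conclusion.** The concern holds. The primary test of each co-primary domain is valid but less efficient than baseline adjustment, and the adjusted model already in the plan has no stated role. Under the main assumptions (change SD 1.25, equal variances, 56 evaluable, alpha 0.025), adjusting for baseline CRQ alone adds about 11, 6 and 4 points of power at r = 0.5, 0.7 and 0.8. The size is uncertain because the documents give neither the SD nor r. It falls as r rises, and roughly to nothing if the three-month SD is 1.2 times baseline and r is 0.7 to 0.8. The full model on complete cases can do worse than the t-test: with 4 dropped and no prognostic value in the extra covariates, 75% at r = 0.7 and 72% at r = 0.8. The change is worth making, but the plan is not invalid without it.

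**What to change.** In both copies of the paragraph (Aims, purpose, or objectives; Analysis Plan):

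1. Name one primary analysis for each CRQ domain: a linear model of the three-month score on arm and the baseline score of the same domain.
2. Label the t-test on change as supportive, so that the primary model governs if they differ.
3. Put age, mMRC and FEV1 in a secondary model. Alternatively, keep them in the primary model with a rule that nobody is dropped for a missing covariate, for example simple imputation of the baseline covariate without reference to arm.

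Settle this before any three-month comparison by arm is seen.

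The cost is a wording change in two places and, if the covariates stay in, one rule. No new data are needed. Baseline adjustment uses one degree of freedom. Keeping the three covariates uses three more and, at SD 1.25 and alpha 0.025, about 2 to 3 points of power if they are not prognostic.

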A home-based intervention to promote mindful breathing awareness through pursed-lip breathing

training for COPD patients

NCT04517500

June 8, 2021

General Study Information

Principal Investigator: [name]

Study Title: A home-based intervention to promote mindful breathing awareness through pursed-lip breathing training for COPD patients, IRB19-012772

Protocol version number and date: June 8, 2021, Version 3

Research Question and Aims

Hypothesis:

We hypothesize that providing COPD patients with a mindful breathing module that is easy-to-use, prompts them to complete daily mindful breathing practice, and provides feedback will improve their breathing mechanics, emotional awareness, increase the time that they spend in heart rate coherence, and improve their quality of life.

Aims, purpose, or objectives:

The primary outcomes of the study are changes in breathlessness and emotions. Changes from baseline to three months on the two primary outcomes will be compared between the study arms using two-sample, two-sided t-tests with 5% type I error rates. Means, SDs, medians, ranges, and frequency distributions will be reported and plotted over time by study arm. Linear models will be used to assess the impact of treatment arm on three-month outcomes after adjusting for the corresponding baseline measure and other variables related to the outcome (age, degree of breathlessness at baseline using the mMRC dyspnea, and FEV1).

Background:

COPD:

COPD is a progressive lung disease that makes breathing difficult. Breathlessness usually worsens over time and eventually may make it difficult for people to carry out regular, simple daily activities, and cause anxiety and depressive symptoms. (8,35) In the United States COPD is the fourth leading cause of death and continues to increase.(2-6) It is also the third leading cause of hospital readmission in the US. There are currently an estimated 16 million Americans diagnosed with COPD(36) and many millions more who are believed to have the disease and not know it.37,38 It is estimated that the direct costs of COPD in the United States are \$29.5 billion and the indirect costs \$20.4 billion.(39)

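### The two co-primary outcomes are sized at alpha 0.025 but tested at two-sided 5%, and no rule says whether one or both must succeed

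*Combined protocol and SAP*

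**What the plan says.** The Sample Size section (under Data Analysis) states that "sixty two participants will provide 80% power to detect 1 point of change", and that this holds "in the two co primary outcomes (breathlessness and emotion as measured by the CRQ) with an alpha of 0.025". It does not say whether 0.025 is one- or two-sided, or whether it is half of 0.05.

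The Analysis Plan, immediately after it, compares the three-month changes in the two arms using "two-sample, two-sided t-tests with 5% type I error rates". The Aims paragraph says the same.

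On the status of the outcomes, the Analysis Plan says only this: "The Domains Dyspnea (breathlessness) and Emotions are the two co primary outcomes". Neither the Aims nor the Data Analysis section gives a multiplicity adjustment, a testing order, or a statement of how many of the two outcomes must be significant.

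**The concern.** Two significance levels are attached to the same pair of outcomes. With two primary outcomes, the most natural reading of 0.025 is 0.05 divided by two, which suits a design where success on either outcome counts. The stated test rule does not apply that division.

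The term co-primary does not resolve this. It can mean that both outcomes must succeed, in which case 5% each is valid. It can also be used loosely for two outcomes, either of which may carry the claim.

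Suppose one domain gives p = 0.03 and the other is not significant. If either outcome is enough, the phase is positive at 5% per test and negative under the split. If both are required, it is negative at any of these levels. As written, the choice could be made after the data are seen.

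**Working it through.** **Inputs.** From the documents: 2 primary outcomes; alpha 0.025 (Sample Size); two-sided 5% (Aims, Analysis Plan); 62 participants; 80% power; 1 point; equal allocation, so 31 per arm. Not in the documents, therefore assumed: the SD of change, and the correlation ρ between the two test statistics (0 to 0.9 shown; 0 is an extreme for two domains of one questionnaire).

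**1. Does N = 62 show which alpha was used?** Take 80% as power per outcome and 1 point as the between-arm difference in change. The text confirms neither. The normal approximation gives SD = 1 / [(z_crit + z_0.80) × √(2/31)].

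- Two-sided 0.025: 1 / [(2.241 + 0.842) × 0.254] = 1.28; the exact t-test gives 1.25.
- One-sided 0.025 (same critical value as two-sided 0.05): 1 / [(1.960 + 0.842) × 0.254] = 1.41; the exact t-test gives 1.38.

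With no SD stated, 62 cannot be reproduced from the plan's own inputs. It fits either alpha, so it does not show which was meant.

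**2. Error rates when neither outcome has a true effect.** For ρ = 0:

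- either at 5% each: 1 − 0.95² = 9.75%
- either at 2.5% each: 1 − 0.975² = 4.94%
- both at 5% each: 0.05² = 0.25%

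For ρ > 0, with Z₁ and Z₂ bivariate normal, the either-outcome error is 1 − P(|Z₁| < c, |Z₂| < c), with c = 1.960 or 2.241.

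| ρ | Either, 5% each | Either, 2.5% each | Difference | Both, 5% each |
|---|---|---|---|---|
| 0 | 9.75% | 4.94% | 4.81% | 0.25% |
| 0.5 | 9.07% | 4.65% | 4.43% | 0.93% |
| 0.7 | 8.35% | 4.30% | 4.05% | 1.65% |
| 0.9 | 7.04% | 3.62% | 3.42% | 2.96% |

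Differences are from unrounded values. Each is the share of null phases in which the two either-outcome rules give opposite verdicts. Simulated t-tests at 31 per arm gave 9.7%, 9.2%, 8.4% and 7.0% for the first column.

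**3. Power at 31 per arm, 1-point difference** (noncentral t with 60 df; simulation where two outcomes are involved, both shifting by 1 point).

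| Quantity | SD 1.25 | SD 1.38 |
|---|---|---|
| Per outcome, two-sided 0.025 | 80% | 71% |
| Per outcome, two-sided 0.05 | 87% | 80% |
| Holm, per outcome (ρ 0.9 to 0) | 83.4% to 85.8% | 75.0% to 77.5% |
| Both significant at 0.05 (ρ 0 to 0.9) | 76.2% to 83.5% | 64.2% to 75.1% |

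Checks at ρ = 0 and SD 1.25: joint power is 0.873² = 0.762. Holm is 0.800 + (0.873 − 0.800) × 0.800 = 0.858. If only one outcome shifts, Holm gives 80% (SD 1.25) or 71% (SD 1.38).

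**The case against.** The strongest reply is that the two statements can be reconciled. The Analysis Plan does not say 5% for each outcome. If 5% is the overall level and 0.025 the share per outcome, the plan is consistent and only loosely worded. This is possible, but it strains against the plural, rates, attached to the t-tests. It would also need the same edit, because a reader following the text would test each outcome at 5%.

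Two further points stand in part. If 0.025 is one-sided, it equals two-sided 0.05 for each test and the mismatch is one of labelling. Error across the two outcomes is then still uncontrolled when either is enough. If both outcomes must succeed, nothing is inflated. The plan does not say that either reading applies.

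It is also fair that the power figures rest on unstated inputs. The SDs of 1.25 and 1.38 assume that 80% was power per outcome and that both domains have the same SD. If 80% was meant as joint power, those SDs do not follow. The contradiction and the missing success rule depend on none of this.

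**Conclusion.** The concern holds and should be fixed before analysis. The plan gives two unreconciled significance levels for its primary outcomes and no rule for primary success. That conclusion needs no assumption.

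The size of the harm depends on the unstated rule. If either outcome is enough and each is tested at 5%, the false positive rate per phase is 7.0% to 9.75%, roughly twice the 3.6% to 4.9% under the split. The lower ends apply at ρ = 0.9 and the upper ends at ρ = 0. If both are required, type I error is at most 3.0% with neither outcome affected over the same range, and the open question is joint power. Confidence is high that the plan is contradictory and incomplete; actual inflation is established only under the either-outcome rule.

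**What to change.** State the success rule, then use one matching alpha and sidedness in the Aims, Sample Size and Analysis Plan.

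- **Either outcome is enough** (fits 0.025 as a split of 0.05): replace the 5% level with two-sided 2.5% per outcome, or with Holm at a familywise two-sided 5% within each phase. Under Holm, the smaller p-value is compared with 0.025 and, if it passes, the other with 0.05.
- **Both outcomes are required**: keep two-sided 5% each, say that both must be significant, and report joint power with the assumed SD and correlation.

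In either case, say whether 0.025 is one- or two-sided, state the SD, and say whether 80% is per outcome or joint.

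**Cost.** Wording in three places. Under the split reading (SD 1.25), two-sided 2.5% keeps the stated 80% per outcome with 62 completers, and Holm does a little better if both outcomes shift. Under the one-sided reading (SD 1.38), power falls from 80% to 71%, about 9 points, and holding 80% needs 76 completers. If both outcomes are required, 80% joint power needs 58 to 68 completers (SD 1.25) or 70 to 82 (SD 1.38), for correlations from 0.9 down to 0.
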